13.8.6 Prognostic Effect of T-cell infiltration

The prognostic effect of infiltrating CD8+ T-cells within the tumor microenvironment will be investigated for each treatment arm. Each patient will be retrospectively classified according to pre-treatment infiltration (positive or negative). Clinical response (CR or PR vs. SD/PD/Unevaluable) will be compared according to infiltration using Fisher's exact tests.

Paired biopsies are mandated in the colorectal arm and also in lung cancer patients that receive liver directed radiation unless there are concerns regarding safety. To give a sense of power for studies to be done on paired tissue, differences will be taken for all measures and the hypotheses is that biomarkers if PD-L1 expression and T-cell infiltration will increase (measured as a continuous quantitative variable) post therapy. Thus, assuming that within each cohort we will obtain post treatment biopsies of at least 25 patients, using a two-sided 0.05 level paired t-test there is at least 80% power to detect a 0.59 SD change in mean of a quantitative correlative parameter using a two-sided test with 5% type I error. Quantitative measure will be transformed to attain normality or appropriate non-parametric tests will be conducted. Power for these tests will be further improved if a greater percentage of paired biopsies are obtained. We will obtaining biopsy samples from participating sites as the trial proceeds and will continuously monitor the percentage of patients for whom a post treatment biopsy is not obtained so we can try to address any issues or questions regarding this. Our plan is to pursue paired tissue analyses separately within each cohort, but since a goal of the study is to more generally evaluate the impact radiation on PD-L1 expression and tumor infiltrating lymphocytes, if needed we can consider analyses that combine data from the 2 cohorts of patients if numbers are not sufficient in the individual cohorts.

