1.2 Secondary Objectives

NSCLC Cohort

- To estimate median progression-free survival and overall survival
- To determine local control within the irradiated field(s) and abscopal response rates
- To evaluate associations between PD-L1 expression as well as levels of infiltrating CD3+, CD8+ T-cells and overall response
- To explore changes in changes in PD-L1 expression, circulating T-cell populations, T-cell infiltration, RNA expression, spatial relationship of immune markers, and mutational burden as a result of low or high dose radiation

Colorectal Cohort

- To estimate median progression-free survival and overall survival
- To determine local control within the irradiated field and abscopal response rates
- To evaluate associations between PD-L1 expression as well as levels of infiltrating CD3+ CD8+ T-cells and overall response
- To evaluate changes between PD-L1 expression as well as levels of infiltrating CD3+, CD8+ T-cells induced by targeted low or high dose radiation
- To explore changes in changes in circulating T-cell populations, T-cell infiltration, RNA expression, spatial relationship of immune markers, and mutational burden as a result of low or high dose radiation

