9. BIOMARKER, CORRELATIVE, AND SPECIAL STUDIES

Introduction

Correlative sciences will include mandatory pre treatment biopsies or archival tissue in all patients to use immunohistochemistry to analyze PD-L1 expression by immunohistochemistry as well as infiltration of CD3+, CD4+, CD8+ T-cells as a predictor of response to combined checkpoint blockade either alone or in combination with lower or higher dose radiation. The biopsies should be taken from the lesion that will be irradiated in the colorectal cohort (cohort 2), and this is also encouraged in the lung cancer cohort (cohort 1), although not mandatory. Although not mandatory in all patients, repeat biopsies should be obtained in cohort 1 patients that receive liver directed radiation therapy.

Additional biopsies following cycle 2 are required of the irradiated lesion in patients with colorectal cancer (cohort 2) to evaluate the effect of radiation on the tumor microenvironment. In both cohorts, additional biopsies taken outside of the radiation field before and after radiation treatment are encouraged when feasible to evaluate abscopal effects on the molecular and cellular level.

Exploratory studies will also be performed on biopsy tissue to examine the relationship between mutational burden and outcome and also correlate the transcriptome with protein expression and evaluate tumor cell composition with flow cytometry. Multiplex immunofluorescence will be used to evaluate spatial relationships between immunologic factors in the tumor microenvironment. Peripheral blood will be obtained before treatment and after one cycle of study treatment for cytokine and PBMC analyses.

Assays will be conducted by the **Cancer Immune Monitoring and Analysis Centers (CIMAC)**, supplemented by assays performed at **DFCI and UC Davis Medical Center**. The following is a summary of assays and scientific objectives that will be performed on the samples collected from this study as approved by the CIMAC leadership:

Priority	Biomarker Name	Assay (CLIA: Y/N)	Use in protocol (Integral, Integrated or exploratory?) Purpose	Sample types and Time points of sample collection		Mandatory optional?
1	PD-L1	IHC (CLIA: Y)	
 • Integrated • To identify biomarkers of response 	Tumor FFPE	Baseline, On treatment	M

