
A: MEDI4736(durvalumab): Administered intravenously at a dose of 1500mg every 4 weeks for a maximum of 13 doses.
 
B: Tremelimumab: Administered intravenously at a dose of 75mg every 4 weeks for a maximum of 4 doses.
 
C: Radiation therapy: Administered only on week 2 for Arm A (high dose radiation) and every 4 weeks for a maximum of 4 times in ARM B (low dose radiation)
 
a: Albumin, alkaline phosphatase, total bilirubin, bicarbonate, BUN, calcium, chloride, creatinine, glucose, LDH, phosphorus, potassium, total protein, SGOT [AST], SGPT [ALT], sodium. Also Also amylase, creatinine clearance, gamma glutamyltransferase, lipase, and magnesium,CPK, TSH. Free T3 or free T4 also measured if TSH is abnormal or if there is clinical suspicion of an AE related to the endocrine system..
 
b: Serum pregnancy test (women of childbearing potential). Women of child-bearing potential must have a negative serum beta-HCG pregnancy test during screening and a negative urinebeta-HCG pregnancy test within 24 hours of starting treatment.
 
c: Every 12 weeks during weeks 12-52 and then 30,60, 90 days after discontinuation
 
d: Every 12 weeks
 
e: Every 4 weeks
 
f: At baseline (screening) and then as clinically indicated.
 
g: Abnormal findings should be repeated and require appropriate clinical evaluation.Normal EKGs do not require repeating.
 
h: If screening laboratory assessments are performed within 3 days prior to Day 1 (first infusion day), they do not need to be repeated at Day 1.
 
i: Archival tissue may be used in place of biopsy in this cohort.
 
j: To be performed week 7 or 8. Optional in patients with irradiated lesions outside the liver. For patients who receive radiation to the liver, this second biopsy is required unless unsafe to perform.
 
k: CT Chest, Abdomen, and Pelvis (CAP)
 
l: During scheduled history and physical exams and during monitoring of AE's, attention should be paid to the side effects resulting from radiation and any potential enhancement of these due to the administration of immunotherapy.
 
m: Negative serologies over the preceding year may replace screening study
 
o: when off treatment for reasons other than progression after week 7-8, until week 52.
 
p: Vital signs timepoints for infusions are pre-dose, every 30 minutes; post-dose 30 and 60 minutes (+/- 10 minutes)
 
q: PRO-CTCAE items to be completed at baseline, every 2 weeks for 8 weeks and then every 4 weeks for a total of 8 cycles. All patients on any arm of study will answer the same list of PRO-CTCAE questions.
															

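### The paired-biopsy test in 13.8.6 measures change on drugs plus radiation, implicitly averaged over both doses, so it cannot attribute a change to radiation or to a dose.

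*Combined protocol and SAP*

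**What the plan says.** Section 1.2 lists for the colorectal cohort: "To evaluate changes between PD-L1 expression as well as levels of infiltrating CD3+, CD8+ T-cells induced by targeted low or high dose radiation". Section 13.8.6 holds the only analysis of tissue pairs. It states that "Paired biopsies are mandated in the colorectal arm and also in lung cancer patients that receive liver directed radiation" (with a safety exception), gives power "assuming that within each cohort we will obtain post treatment biopsies of at least 25 patients, using a two-sided 0.05 level paired t-test", and concludes that "there is at least 80% power to detect a 0.59 SD change in mean of a quantitative correlative parameter". On the unit of analysis it says "Our plan is to pursue paired tissue analyses separately within each cohort", and it allows the two cohorts to be merged if numbers are short. No tissue-pair analysis by dose arm is described. The by-arm wording in 13.8.5 and 13.8.6 belongs to the prognostic Fisher tests.

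Both drugs are given in weeks 1 and 5, radiation starts in week 2, and the second biopsy is at week 7 or 8 (Sections 5.1 and 10). The colorectal cohort is randomised 1:1 to high or low dose, with no radiation-free arm (4.3.3). In NSCLC the second biopsy is required only after liver radiation. Pairs from outside the field are encouraged, not mandated (Section 9).

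On baseline tissue, Section 9 says the colorectal biopsy should come from the lesion to be irradiated. Section 3.1.12.2 softens this to when possible, and accepts an archival sample under 3 months old if a fresh biopsy is not feasible at acceptable risk. Section 9.1.1.1 accepts archival tissue if nothing fresher can be obtained. Footnote i of the Cohort 2 calendar is unconditional: "Archival tissue may be used in place of biopsy in this cohort".

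**The concern.** The objective asks what low or high dose radiation induces. A pre/post difference in patients who all received two checkpoint inhibitors before the second biopsy contains the drug effect, and no mandated unirradiated pairs exist to subtract it. Averaging the two doses also removes the dose question, although Section 2.3 cites animal data suggesting that low dose per fraction may recruit T cells better than higher doses.

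A significant result could therefore be reported as radiation-induced when the drugs produced it, and an effect confined to one dose could be diluted below detection. The biopsies are invasive and mandated, so it matters what conclusion they can support.

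**Working it through.** **Inputs.** From 13.8.6: 25 pairs, two-sided 0.05, paired t-test, 0.59 SD. From 13.4.1: 30 colorectal patients per dose. Effects are in units of the SD of the paired difference.

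**1. The plan's own figure.** Power = P(|T| > t(0.975, n−1)), with T noncentral t on n−1 df and noncentrality d√n. For n = 25 and d = 0.59 the noncentrality is 0.59 × 5 = 2.95, and power is 80.8%. Exactly 80% is reached at d = 0.584. The stated figure reproduces.

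**2. The same test within a dose arm.** If the 25 are per disease cohort and split about evenly:

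| Pairs | Power at 0.59 SD | Change detectable with 80% power |
|---|---|---|
| 25 | 80.8% | 0.584 SD |
| 13 | 50% | 0.85 SD |
| 12 | 46% | 0.89 SD |

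**3. Dilution by pooling (assumed effects).** Suppose one dose (13 pairs) shifts the marker by 0.59 SD and the other (12 pairs) by 0. The pooled mean is (13 × 0.59 + 12 × 0)/25 = 0.307. Mixing the arms raises the variance to 1 + [13 × (0.59 − 0.307)² + 12 × 0.307²]/25, about 1.09. The standardised shift is then about 0.29, and power is about 29%.

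**4. Attribution (assumed drug shift, radiation effect zero, 25 pairs).**

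| Drug shift | Test significant |
|---|---|
| 0.2 SD | 16% |
| 0.3 SD | 30% |
| 0.4 SD | 48% |
| 0.5 SD | 67% |

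The documents give no value for this shift.

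**5. Randomised high- versus low-dose contrast of change scores.** Two-sample t, df n1 + n2 − 2, noncentrality d/√(1/n1 + 1/n2):

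| Pairs per arm | Power at 0.59 SD | Difference detectable with 80% power |
|---|---|---|
| 12 v 13 | 29% | 1.17 SD |
| 25 v 25 | 53% | 0.81 SD |
| 30 v 30 (all 60 paired) | 61% | 0.74 SD |

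**6. Time from radiation to biopsy.** Arm A has one course starting in week 2 and lasting up to 10 days, so biopsy at week 7 or 8 falls about 4 to 6 weeks later. Arm B has its second course in week 6, so biopsy falls about 1 to 2 weeks later.

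**7. Baseline from another lesion (assumed).** If 30% of baselines come from sites that all differ by 0.5 SD in one direction, the mean shift is 0.3 × 0.5 = 0.15 SD, and upper-tail rejection is about 11% against a nominal 2.5%. Across 20% to 50% of pairs and 0.3 to 0.8 SD (mean shift 0.06 to 0.40 SD) the range is 5% to 48%. If 30% of pairs are mismatched and the site differences vary in direction (mean zero, SD 0.5), simulation gives 2.4%, so there is no inflation.

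**The case against.** - **Pooling is not stated.** The sentence in 13.8.6 is offered as an indication of power and is not a full specification. Sections 13.8.3 and 13.8.4 use the word cohort for sizes of 30 and 40, which are arm sizes. On that reading 25 is 25 of 30 per arm, and 0.59 SD is already the per-arm figure. This partly stands: a reader might infer that the plan declares pooling, and it does not. However, the later reference in 13.8.6 to two cohorts points to disease cohorts, and no by-dose tissue analysis appears anywhere. Section 9 does plan arm differences for the blood CyTOF data.
- **Lesion matching is addressed.** A reader might infer that nothing asks for the same lesion. Section 9 does ask for it in colorectal patients, and 3.1.12.2 makes archival tissue a fallback. What stands is that the passages disagree and the calendar footnote carries no condition.
- **Combined-treatment wording exists.** Sections 2.5 and 9 in places describe effects of radiotherapy plus dual blockade, and the hypothesis in 13.8.6 is an increase after therapy. But Section 1.2 says induced by radiation, and 13.8.6 itself gives the impact of radiation as a study goal.
- **The dose contrast does not show induction.** A reader might infer that the randomised contrast settles the objective. It does not: if both doses induce the same change, the contrast is zero. It also has low power, and biopsied patients are a post-randomisation subset. This stands in full.
- **Limited reach.** No primary endpoint or stopping rule depends on these markers. This also stands.

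**Conclusion.** The concern holds in limited form. The power arithmetic is correct; the mismatch is between what the test estimates and what the objective claims. The planned result is change on combined drugs and radiation, implicitly averaged over two regimens. It can be attributed neither to radiation nor to a dose.

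If the 25 pairs are per disease cohort, the detectable change within a dose arm is 0.85 to 0.89 SD, not 0.59 SD. If they are per arm, 0.59 SD applies to each arm and the plan only needs to say so. Attribution to radiation fails on either reading.

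The rejection rates of 16% to 67% rest on an assumed drug shift of 0.2 to 0.5 SD and illustrate sensitivity. They are not estimates of this trial's error rate. The lesion-mismatch rates likewise depend on an assumed frequency and size, and on site differences running in one direction. The documents establish none of these.

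**What to change.** In Section 13.8.6:

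- (a) Report the paired change by randomised dose arm with confidence intervals. State whether 25 is per disease cohort or per arm, and give the per-arm detectable change.
- (b) Add the randomised high- versus low-dose comparison of the on-treatment value, adjusted for baseline, as a descriptive comparison of regimens. State that it addresses a dose difference and not induction, that power is low (about 1.17 SD detectable with 12 versus 13 pairs, about 0.74 SD if all 60 are paired), that biopsied patients are a post-randomisation subset, and that the interval from radiation to biopsy differs by arm.
- (c) Describe the pre/post result as change on combined treatment, and align the Section 1.2 objective with that.
- (d) Reconcile 3.1.12.2, the Section 9 introduction, 9.1.1.1 and the Cohort 2 calendar footnote on baseline tissue. Show same-lesion pairs separately from archival or other-lesion pairs. The Appendix C tissue shipping record already asks for lesion location.

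Any error rate for a drug shift or lesion mismatch should be given as a range with its assumptions.

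The cost is wording and a little analysis, with no extra biopsies. The downside is fewer pairs in the same-lesion set and a less favourable stated detectable change.

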13.8.7 Exploratory Analysis of PRO-CTCAE

The PRO-CTCAE data will be evaluated for data quality, to characterize baseline symptom status of patients on study and the change over time, to explore the development of symptomatic AEs and the change over time, and to explore the patient scores with other relevant clinical information including, but not limited to clinician graded AEs. Feasibility of the electronic collection as well compliance of patients with the reporting will be captured.

13.9 Reporting and Exclusions

13.9.1 Evaluation of Toxicity

All patients will be evaluable for toxicity from the time of their first treatment with MEDI4736 and tremelimumab with or without RT.

13.9.2 Evaluation of Response

All patients included in the study must be assessed for response to treatment, even if there are major protocol treatment deviations or if they are ineligible. Each patient will be assigned one of the following categories: 1) complete response, 2) partial response, 3)

stable disease, 4) progressive disease, 5) early death from malignant disease, 6) early death from toxicity, 7) early death because of other cause, or 9) unknown (not assessable, insufficient data). [Note: By arbitrary convention, category 9 usually designates the “unknown” status of any type of data in a clinical database.]

All of the patients who met the eligibility criteria (with the possible exception of those who received no study medication) should be included in the main analysis of the response rate. Patients in response categories 4-9 should be considered to have a treatment failure (disease progression). Thus, an incorrect treatment schedule or drug administration does not result in exclusion from the analysis of the response rate. Precise definitions for categories 4-9 will be protocol specific.

All conclusions should be based on all eligible patients. Subanalyses may then be performed on the basis of a subset of patients, excluding those for whom major protocol deviations have been identified (*e.g.*, early death due to other reasons, early discontinuation of treatment, major protocol violations, etc.). However, these subanalyses may not serve as the basis for drawing conclusions concerning treatment efficacy, and the reasons for excluding patients from the analysis should be clearly reported. The 95% confidence intervals should also be provided.

REFERENCES

References: (Provide references for cited data and key background/concepts. Verify all references.)

1. Siegel, R.L., K.D. Miller, and A. Jemal, *Cancer statistics, 2015*. CA Cancer J Clin, 2015. **65**(1): p. 5-29.
2. Delbaldo, C., et al., *Benefits of adding a drug to a single-agent or a 2-agent chemotherapy regimen in advanced non-small-cell lung cancer: a meta-analysis*. JAMA, 2004. **292**(4): p. 470-84.
3. Hanna, N., et al., *Randomized phase III trial of pemetrexed versus docetaxel in patients with non-small-cell lung cancer previously treated with chemotherapy*. J Clin Oncol, 2004. **22**(9): p. 1589-97.
4. Borghaei, H., et al., *Nivolumab versus Docetaxel in Advanced Nonsquamous Non-Small-Cell Lung Cancer*. N Engl J Med, 2015. **373**(17): p. 1627-39.

APPENDIX A PERFORMANCE STATUS CRITERIA

ECOG Performance Status Scale		Karnofsky Performance Scale	
Grade	Descriptions	Percent	Description
0	Normal activity. Fully active, able to carry on all pre-disease performance without restriction.	100	Normal, no complaints, no evidence of disease.
		90	Able to carry on normal activity; minor signs or symptoms of disease.
1	Symptoms, but ambulatory. Restricted in physically strenuous activity, but ambulatory and able to carry out work of a light or sedentary nature (e.g., light housework, office work).	80	Normal activity with effort; some signs or symptoms of disease.
		70	Cares for self, unable to carry on normal activity or to do active work.
2	In bed <50% of the time. Ambulatory and capable of all self-care, but unable to carry out any work activities. Up and about more than 50% of waking hours.	60	Requires occasional assistance, but is able to care for most of his/her needs.
		50	Requires considerable assistance and frequent medical care.
3	In bed >50% of the time. Capable of only limited self-care, confined to bed or chair more than 50% of waking hours.	40	Disabled, requires special care and assistance.
		30	Severely disabled, hospitalization indicated. Death not imminent.
4	100% bedridden. Completely disabled. Cannot carry on any self-care. Totally confined to bed or chair.	20	Very sick, hospitalization indicated. Death not imminent.
		10	Moribund, fatal processes progressing rapidly.
5	Dead.	0	Dead.

APPENDIX C Guidance Document for Research Blood Samples

I. Research blood Sample Requirements:

- ❖ 4 -5 lavender top (EDTA), 6 ml vacutainer tubes, should be collected at each time point, following the protocol, referring to section, 10. Study Calendar.
- ❖ It is important that each tube be filled to at least 5ml, to ensure sufficient sample volume.
- ❖ Vacutainer tubes should be immediately inverted 5 times

Sites may either process PBMCs on site, following standard protocols and ship frozen pellets and plasma separately (**preferred method**) or immediately express ship unprocessed vacutainer tubes using an overnight courier, ex. Fed Ex. **The integrity of the blood samples requires they be processed within 24 hours of collection.**

II. Research Sample Shipping Directions:

1. Complete the **Blood Sample Shipping Record** (Template on next page) and include a copy of it with the sample shipment. Please enter the specific information in the highlighted areas.
2. Email the completed **Blood Sample Shipping Record** to [contact], providing notification of the shipment and include in the body of the email the shipping/tracking information (ex., FedEx tracking #xxxx).
3. Do not draw or ship samples the day before a weekend or

Unprocessed EDTA tubes: must be shipped on the day of collection

Samples are to be **shipped overnight, Monday-Thursday ONLY**, at ambient temperature, by overnight carrier, such as FedEx or UPS.

Processed samples: it is suggested to batch ship these samples at a time agreed upon by the collection site and DFCI.

PBMCs-Ship overnight, Monday-Thursday ONLY, using cryotanks containing liquid nitrogen or a styrofoam box containing dry ice, using appropriate labels, following all safety/shipping regulations. Shipments must be made by an overnight carrier, such as FedEx or UPS. Cryotanks have temperature monitors connected to an alarm system at Cryoport headquarters. Shipping temperature should be around -150C. Please contact cryoport via email at [contact] or at [name] for further information re: the cryotanks or temperature recorders.

Plasma-Ship overnight, Monday-Thursday ONLY, using a styrofoam box containing dry ice, using appropriate labels, following all safety/shipping regulations. Shipments must be made by an overnight carrier, such as FedEx or UPS.

Ship Samples to the address on the top left corner of the Blood Sample Shipping Record
Blood Sample Shipping record

Ship To: [name]
Immune Assessment Core Laboratory, (CIO)
Dana-Farber Cancer Institute
[name]
[name]

[contact] or
[contact]

Email: [contact]

From: [Insert name, name, site, site # and address here]

Phone: [Insert phone #]

Email: [Insert email]

Subject ID	[Unique Patient Identifier#]
List of Samples	[example- unprocessed EDTA tubes/frozen PBMCs/frozen plasma # vials, sample date, Cycle time point]
	[example- unprocessed EDTA tubes/frozen PBMCs/frozen plasma # vials, sample date, Cycle time point]

Subject ID	[Unique Patient Identifier#]
List of Samples	[example- unprocessed EDTA tubes/frozen PBMCs # vials, sample date, Cycle time point]
	[example- unprocessed EDTA tubes/frozen PBMCs/frozen plasma # vials, sample date, Cycle time point]

Subject ID	[Unique Patient Identifier#]
List of Samples	[example- unprocessed EDTA tubes/frozen PBMCs/frozen plasma # vials, sample date, Cycle time point]
	[example- unprocessed EDTA tubes/frozen PBMCs/frozen plasma # vials, sample date, Cycle time point]

Please include a copy of this completed document with the shipment and email the recipient above to provide notification

Comments:

Guidance Document for Research Tissue Samples

I. Research Tissue Sample Requirements:

- ❖ Archival, pre-, and on-treatment tissue -Formalin-fixed paraffin embedded block(s) and or unstained/unbaked slides (15-20), stored at room temperature.
 - In general, samples should be placed in fixative at a 10:1 ratio and fixed for at least 24-48 hours but thicker tissue samples may require longer fixation.
- ❖ Optional: If sufficient excess tissue is available at biopsy (generally if more than one biopsy has been performed) then at least 10mg and preferably 20 - 50mg of tumor tissue can be placed in RNAlater (1mL), then snap frozen in liquid nitrogen and stored at -70 to -80°C. These samples can be batched and then shipped overnight on dry ice.
- ❖ All specimens shall be collected following the protocol, referring to section, 10. Study Calendar.

For labelling the blocks please refer to the following guidance;

The block label should be unique and should indicate a) the subject ID and b) time of the biopsy.

examples:

Pre-treatment biopsies should be labeled as: XXXXX-XXX PRE,
Week 7 biopsies should be labeled as: XXXXX-XXX W7
On-treatment biopsies should be labeled as: XXXXX-XXX ONTX
Post-treatment biopsies should be labeled as: XXXXX-XXX POST
where XXXXX-XXX is the unique subject id (EXAMPLE: WI020-027)

II. Research Sample Shipping Directions:

1. Complete the ***Tissues Sample Shipping Record*** (Template on next page) and include a copy of it with the sample shipment. Please enter the specific information in the highlighted areas. Please also include a copy of the Pathology report (de-identified, noting subject # on the report) that correlates to the tissue specimens.
1. Email the completed ***Tissue Sample Shipping Record*** to, [contact].
In the email please include the shipping/tracking information (ex., FedEx tracking #xxxx).
2. Please ship all tissue and or slides following your site specific shipping policies to ensure safe handling, travel and arrival.

Ship Samples to the address on the top left corner of the Tissue Sample Shipping Record
Tissue Sample Shipping Record

Ship To: [name]
Brigham & Women's Hospital
[name]
[name]
[name]

From: [Insert name, name of site, site # and address here]

[contact]

Phone: [Insert phone #]

Email: [contact]

Email: [Insert email]

Subject ID	[Unique Patient Identifier#]
List of Sample(s)	[example- Accession #xxxxx and sample type -1 tissue block]
	[example- Accession #xxxxx and sample type -20 slides]
Timepoint of Sample(s)	[example – pretreatment, on treatment, on progression, archival prior to previous PD-1 therapy (NSCLC cohort only)]
Location from which tissue was obtained (if known).	[Please be as specific as possible: example – irradiated liver lesion, unirradiated liver lesion, irradiated lung lesion, etc.]

Subject ID	[Unique Patient Identifier#]
List of Sample(s)	[example- Accession #xxxxx and sample type -1 tissue block]
	[example- Accession #xxxxx and sample type -20 slides]
Timepoint of Sample(s)	[example – pretreatment, on treatment, on progression, archival prior to previous PD-1 therapy (NSCLC cohort only)]
Location from which tissue was obtained (if known).	[Please be as specific as possible: example – irradiated liver lesion, unirradiated liver lesion, irradiated lung lesion, etc.]

Please include a copy of this completed document, the related path report (if applicable) with the shipment and email the recipient above to provide notification

Comments:

